HUMAN SUBJECTS RESEARCH PROTOCOL

1. PROTOCOL TITLE: Safety, feasibility, and benefits of transcranial direct current stimulation (tDCS) in human subjects with PTSD receiving an exposure-based, behavioral therapy

2. ABSTRACT.

1 2 3

4 5 6

7

8 9

26

Symptoms of posttraumatic stress disorder (PTSD) include intrusive memories about the event, physiological hyperarousal, 10 11 sleep difficulties, and negative alterations to mood and cognitions, all of which can have significant, long-term effects on 12 health and functioning. Evidence-based non-pharmacological, psychotherapies for PTSD exist and are well-established (Lewis et al., 2020). However, there remains room for improvement in outcomes given that a proportion of patients (~50%) do 13 not significantly benefit from treatment (Steenkamp et al., 2015a). The field of non-invasive brain stimulation is rapidly gaining 14 considerable attention as a potential therapeutic for PTSD based on the ability to modulate brain activity in regions associated 15 with the fear response and extinction learning (two critical constructs associated with PTSD pathology and PTSD treatment). 16 While the potential for non-invasive brain stimulation is exciting, research is needed to determine the safety, feasibility, and 17 benefits of non-invasive brain stimulation in human subjects with PTSD. Towards this end, we will conduct a partially double -18 19 blind randomized controlled pilot study of transcranial direct current stimulation (tDCS) vs. a sham condition in a sample of 40 20 adults with PTSD receiving 5 weekly sessions of Written Exposure Therapy (WET), an exposure-based, behavioral 21 psychotherapy for PTSD. 22

23 3. OBJECTIVES/SPECIFIC AIMS/RESEARCH QUESTIONS.

The primary objective of this study is to evaluate the safety, feasibility, and psychological and physiological treatment 24 25 benefits of tDCS, a noninvasive brain stimulation technique, when delivered in combination with WET for PTSD.

27 Specific Aims and Hypotheses:

- Aim 1: To evaluate the safety of tDCS vs. sham when combined with WET. 28
- 29 Hypothesis 1: tDCS can be safely combined with WET for PTSD as indicated by minimal adverse events (AEs) and 30 high tolerability of any observed study related AEs.

Aim 2: To evaluate the feasibility of combining tDCS with WET for PTSD as measured by rates of enrollment, recruitment, 31 and treatment completion. 32

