Frank et al., 2019; van 't Wout et al., 2017). tDCS is of particular interest because of its cost-effectiveness, device portability, and robust safety/side effect profile (Bikson et al., 2016). tDCS involves the use of a low grade (subthreshold), consistent electrical current (1-2 mA) that is typically delivered through two electrodes placed on the scalp for approximately 30 minutes (Nitsche et al., 2008). During stimulation, a current flows between the electrodes passing through the brain to complete the circuit. tDCS is hypothesized to modulate intrinsic neuronal activity by enhancing neuronal resting potential, or altering the likelihood that a neuron will (or will not) depolarize (Rahman et al., 2017). Anodal tDCS increases the excitability of the cortex whereas cathodal tDCS decreases it.

121Safety and Effect of tDCS: There has been a great deal of research on the safety of tDCS, which suggests that the122technique is safe, does not cause permanent or severe damage, or discomfort when used according to appropriate123guidelines (Thair et al., 2017). To date, the use of conventional tDCS protocols in human trials (<40 min, <4 mA) has not	124produced any reports of Serious AEs or irreversible injury across over 33,000 sessions and 1,000 subjects with repeated

- 125 sessions (e.g., Bikson et al., 2016). These results comprise 126 a diverse pool of subjects that includes individuals from potentially vulnerable populations (e.g., those with a 127 psychiatric diagnosis, in pain, and those with neurological 128 conditions). Overall, tDCS has received a "nonsignificant 129 130 risk" determination from different IRBs monitoring a number 131 of trials (Freqni et al., 2015). Typical side effects are minor 132 and transient (e.g., skin irritation, tingling, and minor headaches), with such AEs mitigated by appropriate 133 screening (e.g., exclusion for history of skin condition) and 134 135 the use recommended tDCS guidelines (Bikson et al., 2016; 136 DaSilva et al., 2011; Thair et al., 2017). 137

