Title: Safety, feasibility, and benefits of transcranial direct current stimulation (tDCS) in human subjects with PTSD receiving an exposure-based, behavioral therapy

169 Psychiatry Outpatient Clinics, and the San Antonio community. Participants will be recruited from the South Texas Veterans Healthcare System (SVTHCS) by responding to flyers approved and posted by Public Affairs. Interested 170 171 participants who appear to meet eligibility criteria will be consented and then complete a baseline assessment to 172 determine study eligibility. Eligible participants will be randomized to five weekly sessions of tDCS, or sham, combined 173 with WET for PTSD. tDCS (or sham) will be simultaneously delivered during the writing exposure portion of WET for 30 174 minutes each session. Outcomes to address study objectives will include (1) safety as measured by the adverse events (AE) monitoring logs, (2) feasibility based on study recruitment (number of contacted referrals who were eligible to begin 175 the full baseline assessment over the total number of contacted referrals [will not to include non-contact referrals]). 176 screening (number screened eligible following baseline assessment over the total number of individuals who completed a 177 baseline assessment), and treatment completion (number who completed all 5 sessions over total randomized), and (3) 178 the associated effects of tDCS for PTSD as measured by the PCL-5 and physiological stress response (as measured by 179 180 heart rate and galvanic skin response). Assessments will be collected twice to satisfy study aims at baseline and one-181 month follow-up. Select measures will also be administered during treatment (Table in section 7.3).

183 6.1.1. Randomization. This study will use a partially double-blind randomization design. All participants will be blinded to 184 treatment arm. With the exception of one non-clinical, research team member, all other members of the research team will also be blinded to treatment arm. This approach is so that the PI and research team can be quickly made aware of which 185 186 treatment arm the participant is assigned to in the event of an emergency.

188 7. RESEARCH PLAN.

182

187

189

195

197

198

199

201

202

203

204

205

206

207 208

209

210

211

212

213

214

215 216

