- Next, the study team member will place the HR and GSR device on the individual's non-writing hand and begin 306 monitoring. The participant will then begin the writing exposure and tDCS device will be activated. The Soterix 307 device has standardized programming so that all participants receive the same dose (or sham) and intervention 308 based on the set procedures. The tDCS device will be set at 2.0mA for a total of 30-minutes. Once the "start" 309 button is clicked by the study team member, the device is programmed to gradually ramp up current to the set 310 intensity dose (2.0mA in this study) in the first 30-seconds. As seen in Figure 1, in the active intervention the 311 current will remain at 2.0mA for 30-minutes and then the programmed device will gradually ramp down from 312 2.0mA to 0.0mA in the final 30-seconds. 313

Figure 1. tDCS active condition

As seen in Figure 2, during sham stimulation, participants will experience the gradual current ramp up from 0.0 mA to 2.0mA in the first 30-seconds and then a gradual ramp down from 2.0mA to 0.0mA (30-seconds). The programmed device will automatically repeat this process at the end of the set duration of 30 minutes.

319 Figure 2. tDCS sham condition

320

325

314

315

316

317

318

A study team member will be in the immediate proximity during tDCS (or sham)/written exposure to monitor participant safety and abort the tDCS, if necessary. Clicking the "abort" button will initiate a ramp down of current to 0.0mA. A medical provider will also be available should the participant experience a serious AE or require a higher level of medical care.

56GTSPH3C08UU94FUFQ8ULIG00.docx STRONG STAR Template Version 01/31/22

Title: Safety, feasibility, and benefits of transcranial direct current stimulation (tDCS) in human subjects with PTSD receiving an exposure-based, behavioral therapy

• Following the tDCS (or sham) and writing, a study team member will remove the tDCS and HR/GSR device. Consistent with WET, the participant will meet with a study therapist to review their writing for 15-30 minutes. During this time, the participant will also be monitored for safety prior to leaving the appointment.

7.3.1 Collection of Human Biological Specimens. Females will complete a CLIA-waived hCG pregnancy test at baseline for
 screening eligibility purposes.

332

326

327 328

329

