7.3.2 Data Collection. See Table in Section 7.3 for a summary of the assessments and timing of administration. The data collected in the study will be coded using an assigned number. Hard copies of data collected during the study will be securely stored in locked cabinets at the STRONG STAR offices. Data will be entered into the STRONG STAR database by a member of the research team.

7.3.2.1 Instrumentation. See the table in Section 7.3 for a summary of the assessments and timing of administration. A
 description of each of the assessments can be found at the end of this protocol. Assessments will be administered in
 person whenever possible. However, to accommodate participant schedules and/or instances in which a participant does
 not reside in the local area at the time of a follow-up assessment, we may collect full or partial assessments in person or
 yia phone, video conferencing, and/or electronic data capture using a secure link to the encrypted STRONG STAR
 database. Reasonable efforts will be made to collect all data as described in this protocol, but we expect some

344 participants may not be able to complete part or all of any given follow up assessment.

Title: Safety, feasibility, and benefits of transcranial direct current stimulation (tDCS) in human subjects with PTSD receiving an exposure-based, behavioral therapy

Study Day	Pre/BL	S1	S2	S 3	S4	S5	Post
Informed Consent	R						
Interventions							
tDCS/Sham		R	R	R	R	R	
WET		R	R	R	R	R	
Clinical Interviews	·			•		•	
1. Clinician Administer PTSD Scale-5 (CAPS-5)	S,R						R
2. STRONG STAR Health Questionnaire	S,R						R
3. Health Questionnaire Addendum for tDCS	S,R						
 Self-Injurious Thoughts and Behaviors Interview (SITBI) 	S,R						R
Self-Report Questionnaires		-					
5. PTSD Checklist-5 (PCL-5)	R	R	R	R	R	R	R
6. Patient Health Questionnaire-9 (PHQ)	S,R	R	R	R	R	R	R
7. Generalize Anxiety Disorder-7 (GAD)	R	R	R	R	R	R	R
8. Posttraumatic Cognitions Inventory (PTCI)	R	R	R	R	R	R	R
 Depressive Symptom Index-Suicidality Subscale (DSI-SS) 	S,R	R	R	R	R	R	R
10. Adverse Events Monitoring		R	R	R	R	R	R
11. tDCS Reaction Monitoring		R	R	R	R	R	
12. Demographics Questionnaire	S,R						
13. Life Event Checklist-5 (LEC)	R						R
14. Brief Inventory of Psychosocial Functioning (B-IPF)	R						R
15. Quick Drinking Screen (QDS)	R						R
16. Drug Abuse Screening Test (DAST)	S						
17. Insomnia Severity Index (ISI)	R						R
 Cognitive Emotions Regulation Questionnaire (CERQ) 	R						R

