Only select STRONG STAR Data and Statistics Services personnel have direct access to the data on a "need to access basis"; for example (but not limited to) detecting and repairing data corruption and producing reports not currently within the STRONG STAR system. STRONG STAR Data and Statistics Services also follows the Principals of Least Privilege (POLP). All user activity is tracked and recorded within the system so if any records are added, altered, or viewed the action is recorded and can be recalled for auditing purposes. Access to this information will require a password-protected login available only to authorized STRONG STAR Data and Statistics Services staff.

Every member of the Research Team will be trained and monitored about how to handle and protect both research
records. Furthermore, the Research Team strictly controls access to study data. The STRONG STAR Data Safety and
Monitoring Plan (DSMP) that has been developed in accordance with the National Institutes of Health Office of Human
Research Protection to assure the appropriate clinical safety monitoring of study subjects participating in research will be
used to monitor this study.

377

378**7.4 Statistical Consideration**379

7.4.1 Sample Size Estimation.

381

382

389

Total Required to Consent	50
Estimated Participant Screen Fail / Exclusion (20%)	10
Target Sample Size to be Randomized	40
Estimated Participant Drop Out / Withdrawal after randomization (15%)	6
Expected Treatment Completers	34

7.4.2 Primary (i.e., primary outcome variables) and secondary endpoints (See Table in section 7.3). Adverse event
 (AE) monitoring will address study Aim 1. To assess study feasibility (Aim 2), we will track study recruitment (number of
 eligible referrals/total referrals), enrollment (number of screened enrolled participants/total eligible), and treatment
 (number of participants who completed all 5 WET sessions). The PCL-5 (Weathers, Litz, et al., 2013) will be the primary
 outcome to assess PTSD severity (Aim 3a). Heart rate (HR) and galvanic skin response (GSR) will be used to address
 Aim 3b.

390 **7.4.3 Data analysis.**

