391 Power Analyses: This pilot study is not powered for formal efficacy or mechanistic hypotheses testing. Consistent with 392 research regarding the purpose of a pilot study, our main interests were to evaluate the feasibility of the proposed recruitment, 393 assessment, and treatment protocols, examine safety, and to explore a detectable effect of tDCS across outcomes in 394 preparation for a larger trial (Kraemer et al., 2006; Leon et al., 2011). Although the statistical power of this study is limited, we 395 will perform statistical analyses appropriate for an adequately powered study to identify data analysis issues germane to 396 future planning.

Data Analyses: Prior to developing statistical models, all variable distributions will be examined using frequency distributions,
 scatter plots, and histograms. Statistics such as means or proportions, standard errors, ranges, and estimates of skewness
 and kurtosis will be computed and used as guidelines in the application of analyses. Data transformation procedures may be
 applied to variables with considerable departure from normality.

402

The objectives of this study are to evaluate the safety, feasibility, and PTSD symptom reductions associated with tDCS vs. sham. All statistical analyses will be intent to treat and include all participants randomized at baseline regardless of the statistical analyses will be intent to treat and include all participants randomized at baseline regardless of the

Title: Safety, feasibility, and benefits of transcranial direct current stimulation (tDCS) in human subjects with PTSD receiving an exposure-based, behavioral therapy

extent of study participation. Given the small sample size, we will use a Benjamini-Hochberg Adjustment procedure to mitigate the false discovery rate (two tailed initial p = .05). Analyses will be done SPSS 27 statistical software. As needed, we also have access to SAS 9.4, Stata 14.2, R, and Mplus 8.4 software.

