408 409 Descriptive Statistics to Address Aims 1 and 2: Descriptive statistics will be used to address the safety and feasibility of 410 tDCS when combined with WET. To assess, safety, we will evaluate the frequency, severity, and relatedness of AE based on the STRONG STAR AE monitoring procedures. AE logs will be reviewed and adjudicated with the study team during 411 weekly meetings to evaluate reliable coding and participant safety. [name]. PsvD (PI) and [name] (Co-I: 412 Attending Physician) will also hold one-on-one meetings as needed to mitigate health related AEs and monitor 413 participants. To assess study feasibility, we will estimate recruitment (number of eligible referrals/total referrals). 414 enrollment (number of screened enrolled participants/total eligible), and treatment (number of participants who completed 415 416 all 5 WET sessions). Feasibility data will be used to inform planning for a larger clinical trial.

417

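### Aim 1 safety rests on adverse event monitoring alone: the end-of-session tDCS Reactions form is not named as an outcome and no summary of it is planned

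*Combined protocol and SAP*

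**What the plan says.** Section 3 frames Aim 1 as a comparison of tDCS with sham, and Hypothesis 1 expects few AEs and "high tolerability of any observed study related AEs". Three places then say how Aim 1 is measured or analysed:

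- Section 6 lists the outcome as "safety as measured by the adverse events (AE) monitoring logs".
- Section 7.4.2 says that AE monitoring "will address study Aim 1".
- Section 7.4.3, in the descriptive paragraph for Aims 1 and 2, says "we will evaluate the frequency, severity, and relatedness of AE based on the STRONG STAR AE monitoring procedures".

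The table in section 7.3 schedules a separate instrument, "11. tDCS Reaction Monitoring", as research data at sessions 1 to 5. Section 8.1 says it is completed when each session finishes and gives safety assessment as its purpose. Section 14.2 (item 11) places it under a STRONG STAR SOP and describes one procedure: an elevated item leads to review by a therapist and, if needed, by medical staff.

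AEs themselves are elicited differently. Section 14.2 (item 10) gives an open question about worsening since the previous visit, asked before each session and at the one-month follow-up.

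On analysis sets, section 7.4.3 has one general rule: "All statistical analyses will be intent to treat and include all participants randomized at baseline regardless of the" extent of participation.

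**The concern.** The form is the only self-report scheduled straight after each stimulation or sham run, and both arms complete it. The reactions the protocol expects are minor and short-lived, such as itching, tingling or mild headache. Section 8.1 says it is unclear whether such events are caused by tDCS at all, because many controlled trials found no difference from sham. A by-arm summary of the form speaks directly to that question.

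As the plan is worded, the Aim 1 result can be produced in full without opening these data. It would then depend on which reactions reach the AE log, where the scripted question is open-ended and asked later. Hypothesis 1 is a claim of good tolerability, so the solicited post-stimulation reports should be part of the evidence for it.

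A smaller issue sits beside this. With no safety exception to the all-randomised rule, anyone randomised but never stimulated enters the AE denominator and can only pull down the rate of stimulation-related events.

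**Working it through.** **1. The plan's own flow figures (section 7.4.1).** 50 × 0.20 = 10 screen failures; 50 − 10 = 40 randomised; 40 × 0.15 = 6 dropouts; 40 − 6 = 34 completers. These reproduce exactly. The main point rests on text, not on these figures.

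**2. Text comparison.** Of the three statements of the Aim 1 outcome or analysis (sections 6, 7.4.2, 7.4.3), none names the Reactions form. The mentions of the form in sections 7.3, 8.1 and 14.2 give a schedule, a safety purpose and a review procedure. None gives a score, an analysis variable or a tabulation. The only models with a treatment term are the GLMMs for Aim 3.

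**3. How much data is involved.** Forms = participants × sessions.
- Six dropouts attending no session: 34 × 5 = 170.
- Six dropouts attending four sessions each: 170 + 6 × 4 = 194.
- No dropout: 40 × 5 = 200.

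This counts data with no stated summary. It does not count missed events.

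**4. Timing of the scripted AE question.** It is asked 6 times (sessions 1 to 5 and follow-up). The session 1 asking precedes any stimulation, leaving 5. The next asking comes about one week after sessions 1 to 4, and about one month after session 5 if the follow-up month runs from session 5 (an assumption). Session 5 supplies 34/194 = 17.5% to 34/170 = 20.0% of the forms (40/200 = 20.0% with no dropout).

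**5. What a by-arm table could show.** Assume 1:1 allocation, which is not stated, so 20 per arm. At the 15 to 30 per 100 that section 8.1 gives for the likely, non-serious risks, 20 × 0.15 = 3 to 20 × 0.30 = 6 participants per arm would report one. Exact 95% intervals (Clopper-Pearson) are 3.2% to 37.9% for 3/20 and 11.9% to 54.3% for 6/20. The table would be descriptive only.

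**6. Denominator effect.** If k of 20 in an arm were never stimulated and had no AEs, the all-randomised rate is r × (20 − k)/20, where r is the rate among those stimulated.

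| k | r = 30% | r = 15% | relative loss k/20 |
|---|---|---|---|
| 0 | 30.0% | 15.0% | 0% |
| 3 (six dropouts split evenly) | 25.5% | 12.8% | 15% |
| 6 (all six in one arm) | 21.0% | 10.5% | 30% |

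In the last row, two arms that both truly had 30% would differ by 30.0 − 21.0 = 9.0 points.

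**The case against.** Several things count against a strong reading.

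- **Other routes to the log exist.** Section 5 treats these reactions as AEs ("with such AEs mitigated by appropriate" screening). Section 7.3 says "A study team member will be in the immediate proximity during tDCS (or sham)/written exposure to monitor participant safety". Section 8.1 adds observation after stimulation and AE monitoring at each session. Reported events are documented and flagged forms are reviewed.
- **Governing documents are missing from the file.** The STRONG STAR AE procedures, the SOPs and the Data Safety and Monitoring Plan were not supplied. Any of them may set out how a reaction on the form becomes a logged AE.
- **A comparison by arm is already the aim.** Section 3 and the objectives sentence in 7.4.3 both speak of safety for tDCS against sham.
- **The form is not wholly detached from the endpoints.** Section 7.4.2 refers to the table in 7.3, where the form sits directly after AE monitoring. Section 7.1.6 says every measure serves research, and section 6 introduces its outcomes as an inclusive list.
- **This is a descriptive pilot,** and the forms can be tabulated at any time.

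A reader might infer that acute reactions will go unrecorded, that safety is unmonitored, or that no between-arm safety comparison is intended. The first three items rule those inferences out: the first two are not shown, and the third contradicts the stated aim. What survives is narrower. After its general pointer to the table, section 7.4.2 assigns only AE monitoring to Aim 1. No supplied text carries the by-arm intention over to this form or requires its content to enter the log. Examining safety is also one of the pilot's stated main interests, so choosing the safety summaries in advance is worthwhile.

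**Conclusion.** The point holds as a gap in pre-specification. A safety instrument completed after every stimulation session is left out of the stated Aim 1 outcome, and no summary of it is planned. It affects 170 to 200 forms. Any resulting under-recording of reactions is possible but cannot be shown or sized from the documents.

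The denominator point is secondary. It would be wrong to read the 15% to 30% dilution as the expected effect. It is an upper-bound illustration that assumes 1:1 allocation, that all six expected dropouts were never stimulated, that they had no AEs, and, for 30%, that all six were in one arm. The plan sets dropouts only against treatment completers, so many may have had some sessions. The AE question is also asked at session 1 before stimulation, so unstimulated participants can contribute events. Even the worst case, 30% read as 21.0%, is small beside an exact interval of 11.9% to 54.3%.

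**What to change.** **Main change.** In sections 7.4.2 and 7.4.3, name the tDCS Reactions form as an Aim 1 safety outcome. Summarise it descriptively by arm, both per participant and per session. Report any reaction for each item with its severity, and the proportion with at least one elevated item. Both layers are needed: the threshold for elevated is not in the supplied text, and a table limited to flagged forms could leave out the mild reactions that are most expected. State how reactions on the form enter the AE log, or cite the SOP that says so.

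**Minor change.** In section 7.4.3, exempt Aim 1 AE rates from the all-randomised rule. Use participants with at least one tDCS or sham session as the denominator, and report by arm how many were randomised but never stimulated.

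**Cost.** A few sentences and some extra descriptive tables from data already being collected, with no new visits or measures. Reported AE rates may come out slightly higher with the exposed denominator.

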418 Generalized Linear Mixed Models (GLMM) to Address Aim 3: GLMM will be used to evaluate changes in continuous outcomes associated with tDCS vs. sham. GLMMs are a powerful and flexible statistical extension of linear mixed models 419 420 that can examine outcome variables from different distributions, such as normal (continuous) and binary outcomes. Advantages of likelihood-based regression models over conventional ANOVA include the ability to use data from all 421 participants even if they have only baseline data, relaxation of the assumption of equal variances before and after 422 423 treatment, specification of data distributions other than normal such as Poisson or log-normal, and the ability to analyze 424 longitudinal data in the presence of missing data given the assumption that data are missing at random. GLMM's will 425 include fixed effects of time, treatment (tDCS vs. sham), and the time by treatment interaction. Models will include a priori planned contrasts of mean differences over time and simple effects to evaluate treatment differences at each time point. 426 To inform future studies, we will calculate conventional effect sizes with 95% confidence interval limits (Hertzog, 2008). 427 Hedges' q will be used to calculate continuous outcome effect sizes (e.g., PCL-5). Hedges' q has been recommended 428 over Cohen's d for small samples based on sample size adjustments, yet can be interpreted using the same conventional 429 recommendations as Cohen's d, .20 =small, .50=medium, and .80=large effect sizes (Lakens, 2013). 430 431

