Assessment timepoints are presented in the 7.3 Table. The PCL-5 will be the primary outcome to evaluate changes in 432 PTSD severity from baseline assessment to one-month follow-up, with data points collected during treatment also 433 included in models (Aim 3a). Heart rate monitoring and GSR will be used to evaluate physiological stress arousal during 434 435 the writing exposure task (Aim 3b). Both physiological outcomes will be collected during the writing exposure portion of sessions 1, 3, and 5 to provide before, after, and peak estimates of physiological arousal. Time points of interest for 436 437 physiological outcomes will be the immediate, long-term, and peak effects of tDCS. The immediate effect of tDCS will be 438 defined as changes immediately prior to and after the first written exposure (i.e., change from T_1 to T_2), the third written 439 exposure (change from T_3 to T_4), and the last time participants engage in writing exposure (change from T_5 to T_6). The 440 long-term effect of tDCS will be defined as changes in physiological levels across sessions (session 1 to session 5) prior 441 to engaging in the writing exposure (change from T_1 to T_5) and after the writing exposure (change from T_2 to T_6). The *peak* effect will evaluate change score differences (interaction effect) in the greatest estimate during session 1 to session 5. 442

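### The Aim 3 PCL-5 model lets the arms differ at baseline and does not adjust for baseline, so the exploratory one-month tDCS-versus-sham estimate is unbiased but can be less precise than the collected data allow.

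*Combined protocol and SAP*

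**What the plan says.** All of the relevant text is in Section 7.4.3.

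- The fixed effects are listed in full: models "include fixed effects of time, treatment (tDCS vs. sham), and the time by treatment interaction".
- Baseline is part of the outcome vector. One stated advantage of the method is that it uses "participants even if they have only baseline data". The PCL-5 is to evaluate changes in "PTSD severity from baseline assessment to one-month follow-up, with data points collected during treatment also" in the models.
- The planned contrasts are mean differences over time and "simple effects to evaluate treatment differences at each time point".
- Equal variances are not required: the text cites "relaxation of the assumption of equal variances before and after" treatment as an advantage.
- The intended product is an effect size: "To inform future studies, we will calculate conventional effect sizes with 95% confidence interval limits", with Hedges' g for continuous outcomes.
- The study's status is plain: "This pilot study is not powered for formal efficacy or mechanistic hypotheses testing".

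No baseline covariate and no common-baseline constraint appears anywhere. The text does not say how time is coded, which contrast and SD enter g, or how the interval for g is computed.

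**The concern.** A treatment main effect, with baseline among the time points, gives each arm its own baseline mean. Randomised arms have the same expected mean before treatment, so the model spends information estimating a difference known to be zero in expectation. Neither planned contrast recovers it. The one-month simple effect makes no correction for chance imbalance at baseline, and the change contrast subtracts all of that imbalance whatever the correlation. Simple effects at every time point also include a treatment test at baseline, where any difference is chance.

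What is at stake is the width of the interval around the exploratory PCL-5 effect, which is the Aim 3 result meant to inform a later trial.

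**Working it through.** **Inputs from the documents.** Section 7.4.1: 50 consented, 20% screen failure, 40 randomised, 15% dropout. The flow reproduces: 50 × 0.80 = 40 and 40 × 0.85 = 34. Section 7.3 table: seven PCL-5 points (baseline, before sessions 1 to 5, one month).

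**Assumptions, none stated in the documents.** 1:1 allocation (20 per arm, 17 completing); categorical time; the 3 dropouts per arm leave after session 3; covariance known; correlation ρ of .3, .5 or .7; SD = 1 unless noted.

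**Two-visit formulas.** With n = 20 per arm at baseline and m = 17 at one month, the variance of the arm difference is:

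- simple effect: 2[(1−ρ²)/m + ρ²/n]
- change contrast: 2[(1−ρ²)/m + (1−ρ)²/n]
- common baseline mean: 2(1−ρ²)/m

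At ρ = .5 both planned contrasts give 2(.75/17 + .25/20) = .1132, and the common-baseline model gives 2(.75/17) = .0882. The reduction is .0250/.1132 = 22%.

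**Seven-visit generalised least squares.** SE of the one-month difference in SD units, and the variance cut from the common-baseline model:

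| Structure | ρ | Simple | Change | Common | Cut vs better | Cut vs change |
|---|---|---|---|---|---|---|
| Equal correlation | .3 | .338 | .393 | .325 | 8% | 32% |
| | .5 | .333 | .333 | .293 | 23% | 23% |
| | .7 | .326 | .258 | .240 | 14% | 14% |
| Same, follow-up SD × 1.3 | .3 | .440 | .464 | .422 | 8% | 17% |
| | .5 | .432 | .396 | .380 | 8% | 8% |
| | .7 | .424 | .313 | .312 | 1% | 1% |
| AR(1) | .3 | .343 | .466 | .343 | 0% | 46% |
| | .5 | .343 | .463 | .343 | 0% | 45% |
| | .7 | .340 | .438 | .338 | 1% | 41% |

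In the AR(1) rows ρ is the correlation between neighbouring visits. The baseline-to-follow-up correlation is ρ⁶, at most .7⁶ = .12. Baseline then says little about follow-up, so the simple effect is already nearly efficient and the change contrast is poor.

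**In interval terms.** At the peak (equal correlation, ρ = .5) the 95% half-width goes from 1.96 × .333 = .65 SD to 1.96 × .293 = .57 SD.

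**Cost of estimating the adjustment.** Theory gives a variance inflation of about 1 + 1/(2m−4) = 1 + 1/30. In a two-visit simulation with 17 per arm and the slope estimated, the gain over the better contrast was 6%, 22% and 12% at ρ = .3, .5 and .7 (9%, 25% and 15% with the slope known). At ρ = 0 it was a loss of about 3%.

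**Hedges' g interval.** The conventional half-width, 1.96 × √(2/17 + g²/68), is .67 at g = 0 and .68 at g = .5. It depends only on group sizes and g, so it is the same whichever model is fitted. Dividing the model SE by the sample SD and stopping there goes wrong the other way. In simulation with 17 per arm and ρ of .5 or .7, coverage was about 94% at g = .5 and 91-92% at g = 1.2. Adding g²/(2 df) to the variance brought it to about 95-96%. For scale, at ρ = .5, g = .5 and df = 32 the variance is .293² + .25/64 = .0898, a half-width of .59 against .68.

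**The case against.** The strongest reply is that nothing here is an error. Time, treatment and their interaction form a standard longitudinal model, it suits a stated interest in change from baseline, and the study is an exploratory pilot. That stands as far as it goes. A reader might infer that the planned analysis is biased, or that the sample size needs revisiting. The documents support neither: randomisation protects the estimate, and the 40 rests on participant flow, not on power.

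Second, 23% is a peak. It needs equal correlation, equal variances and ρ near .5, and several plausible structures give 0-8% against the better contrast. That also stands, so 23% should not be read as the expected gain. But the better contrast cannot be picked in advance without knowing the correlation. Within the categorical model with known covariance, the common-baseline estimate is never worse than either contrast.

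Third, constraining the baseline does not by itself narrow the reported interval if a conventional g formula is used. This is correct, and it is why the fix covers the interval as well as the model.

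Fourth, adjusting for baseline as a covariate would drop participants with baseline data only. That conflicts with the plan's rule of analysing everyone randomised and with its stated reason for using a likelihood method. This is correct and rules out that version; the common-mean version keeps them.

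Smaller points:

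- If time were linear (visits at weeks 0-5 and 9, assumed), the planned change contrast has SE .294 and .228 at ρ = .5 and .7, so a constrained categorical model (.293 and .240) offers no advantage there. Contrasts at each time point suggest categorical time, but the plan should say so.
- Section 7.4.1 counts treatment completers, and Section 10.0 schedules a final evaluation for discontinued participants, so more than 34 may have late data. With complete data the large-sample gain at ρ = .5 is 25%.
- The PCL-5 before session 1 also precedes stimulation. Constraining it too would raise the gain to about 12%, 30% and 27% at ρ = .3, .5 and .7 under equal correlation. It appears to follow randomisation and uses a one-week recall window against two weeks at baseline, so I do not count this.

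**Conclusion.** The point holds as one of precision only. Under the assumptions above, a common-baseline model lowers the variance of the one-month difference by about 0-23% against the better planned contrast. Against the change contrast, which the Aim 3a wording suggests, the reduction is 14-32% (equal correlation and equal variances), 1-17% (follow-up SD 1.3 times baseline) or 41-46% (AR(1)). At a correlation near zero it costs about 3%.

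The true figure depends on a correlation, a covariance structure and an SD ratio that the documents do not give, so any quoted gain must name its comparator. The change is worth making because the value is already collected and the interval is what the next trial will use. The planned analysis remains valid without it, and Aims 1 and 2 are untouched.

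**What to change.** In Section 7.4.3:

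1. State that time is categorical and keep baseline PCL-5 in the outcome vector.
2. Constrain the arms to a common baseline mean: seven visit means, with treatment-by-time terms only after baseline and no separate treatment main effect. Do not use the covariate version that loses baseline-only participants.
3. Drop the treatment test at baseline.
4. Name the resulting one-month difference as the between-arm estimate, and report it in PCL-5 points with its model-based 95% CI.
5. If Hedges' g is also reported, define it as that difference over the raw pooled SD of a stated visit, with the small-sample correction. Take its interval from the model SE plus a term for sampling error in the SD, for example g²/(2 df), or from a bootstrap.

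The cost is analysis-plan wording: no new data, visits or participants. The one added assumption, equal arm means at baseline, is supplied by randomisation. The price is about 3% of variance if baseline turns out to be uncorrelated with follow-up.
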